Objective 3: To determine the impact of the HBB Prompt app on HBB skills retention of providers in the intervention site compared with providers in the control site.

1. Primary outcome: comparison of OSCE B scores in intervention (HBB Prompt) vs. control group. (17 out of 23 constitutes a pass score)
 - a. At 0 months, (immediately before and after training)
 - b. At 3 months
 - c. At 6 months (midline)
 - d. And at 12 months (endline)
2. Measures during the 12-month period of intervention in HBB Prompt site and control site at two unannounced visits (4 months, 9 months):
 - i. HBB 2.0 Knowledge check (18 questions)
 - ii. Bag and mask ventilation skills check (score out of 14)
 - iii. OSCE A (score out of 12, 9 out of 12 constitutes pass score)
 - iv. In addition to the OSCE skills checklist as scored by raters, we will use the Augmented Infant Resuscitator (AIR) to objectively measure quality of newborn resuscitation during every ventilation epoch. AIR records time stamped data on ventilation quality, such as presence of air leak or obstruction and ventilation rate (www.air-device.com).
 - b. Data on potential confounders will be collected for each site (volume of deliveries, workload in labor and delivery, burnout, motivation, baseline supervision, experience, previous training, provider level, number of patients/areas each provider is responsible for, length of time provider has been in practice, availability of equipment, availability of an HBB algorithm posted at the bedside.)
 - c. Other clinical outcomes will be collected from the Ministry of Health Birth Register: For each patient: date of birth, time of birth, birth weight, death before discharge, admission to nursery, 1 and 5 minute Apgar scores, resuscitation status at birth and resuscitation outcome.
 - d. Reports generated and presented to each site every 2 months: frequency of practice, number of deliveries, number of infants requiring bagging, fresh stillbirths, neonatal mortality in hospital
3. App analytics
 - a. Pattern of usage
 - i. Which components of the app are being used?
 - training mode, simulation mode, help videos, quizzes
 - b. Frequency (login, page use), purpose device ID
 - i. Is low dose high frequency happening? – Frequent, short duration access?
 - c. Self practice vs. peer or group practice
 - d. Trends for scores for simulations and quizzes

4. We will conduct exit focus group discussions and interviews at both intervention and control sites:

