 - a. For Intervention site providers:
 - i. Facilitators and barriers to implementing and maintaining HBB skills
 - ii. Did HBB Prompt help?
 - iii. Did HBB Prompt meet end-user needs
 - iv. Any suggestions for further improvement
 - v. Feasibility and sustainability of scale-up
 - vi. HBB Prompt specifics: content, interface, navigation, functionality, customizability, usability
 - b. For Control site providers:
 - i. Facilitators and barriers to implementing and maintaining HBB skills
 - ii. Discussion about ideas to facilitate skills maintenance
 - c. For both sites:
 - i. Perception of workload in labor and delivery, burnout, motivation
 - ii. Interviews only: description of baseline supervision, number of patients and areas each provider is responsible for, availability of equipment for practice and for clinical care (e.g. bag-mask ventilator, HBB algorithm)

Randomization

A random sequence generator will be used to determine a random number just prior to the start of phase 2. If the random number is odd, then Itojo will be the intervention site. If the number is even, then Kitagata will be the intervention site.

Study setting

Southwestern Ugandan (Itojo Hospital, Ntungamo District; Kitagata Hospital, Sheema District). Each study site will have HBB practice corners established and equipped with both resuscitation mannequins and resuscitation bag and mask devices.

Study duration

18 months in total, 4 months for phase 1 and 12 months for phase 2 and 2 months for data analysis.

Participant eligibility criteria and enrolment

Study Population Eligibility: We will conduct the study in an area where HBB is recommended as the training program for newborn resuscitation

Inclusion Criteria: Frontline birth attendants involved in the delivery or care of babies in the maternity ward, theater or pediatric wards with a possibility of involvement in newborn resuscitation.

Exclusion Criteria: Health workers providing care in other wards other than maternity and pediatrics.

Enrolment: Using community entry processes, the medical superintendents of each hospital will be approached and requested to allow the study to be conducted in the Hospital. Once consent is obtained from the superintendent, individual frontline birth attendants will be approached and consented to be part of the study before training sessions are conducted.

Data Analysis

Phase 1

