Audio recordings from focus groups and interviews will be transcribed. Transcripts will be reviewed for themes using a grounded theory approach. Data analyses will take place after each iteration of phase 1b to incorporate feedback to improve and adapt each version of the HBB Prompt prototype. At least two investigators will independently read all transcripts at least twice to obtain an overall understanding, identify data codes and ensure that all comments are carefully considered and included. Categories within the themes will then be identified, and any relationships among themes determined. As data are entered into the analyses, categories will continue to be generated, until there is no new data that cannot be categorized under existing codes. When this occurs, it is likely that a range of functions and features of an ideal mobile app as a learning tool for HBB will have been categorized. Further, we will also likely have categorized an assortment of barriers and facilitators to skills maintenance and implementation of HBB Prompt. A similar analytic approach has previously been successfully used in the development of an osteoporosis clinical decision support tool (10).

Phase 2

Comparison of intervention versus control for the following outcomes will be analyzed at each time point using the Mann-Whitney U test:

- Primary outcome: OSCE B score at 12 months
- Secondary outcomes:
 - OSCE B scores at 0, 3, and 6 months
 - At two unannounced site visits (months 4 and 9)
 - Knowledge check score
 - BMV skills check score
 - AIR data
 - Percentage of time with correct ventilation rate
 - Percentage of time with air leak during ventilation
 - Percentage of time with obstructed airway during ventilation
 - Time to effective ventilation
 - OSCE A score

Additionally, comparison of OSCE B score after training at 0 months and at 12 months within each arm using the Wilcoxon-signed rank test

	0 months	3 months	4 months	6 months	9 months	12 months
OSCE B	Pre/post HBB training	x		x		x
OSCE A			x		x	
Knowledge check			x		x	
Bag-mask skills			x		x	
AIR			x		x	

Descriptive statistics compared between intervention and control for:

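### No confounder is scheduled before training: changeable ones such as burnout, motivation and supervision are placed in the intervention year or at exit, yet are compared between hospitals as potential confounders

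*Protocol*

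**What the plan says.** Objective 3, item 2 is headed "Measures during the 12-month period of intervention in HBB Prompt site and control site", and the heading names unannounced visits at months 4 and 9. Within it, item 2b reads "Data on potential confounders will be collected for each site (volume of deliveries, workload in labor and delivery, burnout, motivation, baseline supervision" and goes on through the rest of a 12-variable list.

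Item 4 adds: "We will conduct exit focus group discussions and interviews at both intervention and control sites". Its topics for both sites (item 4c) include "Perception of workload in labor and delivery, burnout, motivation" and, in the interviews, "Interviews only: description of baseline supervision, number of patients and areas each provider is responsible for", together with the availability of equipment, for which the HBB algorithm is given as an example.

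Under Randomization: "A random sequence generator will be used to determine a random number just prior to the start of phase 2". Objective 2, Phase 2a gives the intervention hospital access to the app once training ends.

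In Data Analysis, Phase 2, the schedule table has a month-0 entry for OSCE B only ("Pre/post HBB training") and no row for confounders at any month. The same section plans a descriptive comparison between arms of demographic data and the same 12 potential confounders.

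**The concern.** A variable is useful for judging whether two groups were comparable at the start only if its value could not have been altered by what was later done to one of them. Burnout, motivation, perceived workload and supervision could all plausibly shift over a year of practice targets, app use and two-monthly feedback. If the hospitals differ on motivation at the end of that year, the reader cannot tell whether they differed beforehand or whether the app made the difference. A real difference at the start could equally have narrowed and gone unseen.

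This matters more here than in a trial with many units. There is one hospital per arm, with a minimum of 10 providers in each. Randomising two hospitals cannot be expected to balance anything, so interpretation leans on a description of how the hospitals differed before the app arrived. Values that were never collected at that time cannot be recovered later by an analysis plan.

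**Working it through.** The protocol gives no figure tied to this point, so the check sets the passages side by side.

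**1. Order of events.** The site is drawn just before phase 2. Phase 2 opens with training, and app access follows training. Anything collected at months 4 or 9 or at exit is therefore after both allocation and first access.

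**2. Where the 12 variables of item 2b are placed.**

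| Group | Variables | Count | Occasion named |
|---|---|---|---|
| Also exit topics (item 4c) | workload, burnout, motivation, baseline supervision, patients/areas per provider, equipment, posted algorithm | 7 | Exit; otherwise only the general item 2 heading |
| Fixed provider characteristics | experience, previous training, provider level, length of practice | 4 | General item 2 heading only |
| Datable from records | delivery volume | 1 | General item 2 heading only |

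The total is 7 + 4 + 1 = 12. Item 4c gives the algorithm as an example of equipment; counted that way, the first group has 6 entries.

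**3. Which of these are harmed by late measurement.**
- The four fixed characteristics are not; the app cannot change them.
- Delivery volume need not be, because it can be taken from records for a chosen period.
- Burnout, motivation, perceived workload and supervision are the main exposed items, since each could respond to the app or to feedback.
- Patient load and equipment may change for reasons unrelated to the app, but a value at exit still does not describe the starting state.

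**4. Baseline supervision.** The label refers to the start, but the named occasion is exit from a 12-month phase. What is obtained is a recall over about 12 months, given after a year in which each site received reports every two months.

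**5. What is available before exposure.** OSCE B is measured immediately before and after training and is compared between arms at 0 months. That is a planned pre-exposure comparison of starting skill. It says nothing about supervision, motivation or workload, which may bear on how well skill is retained.

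**6. Where the values are used.** They enter a descriptive comparison. The primary analysis is a Mann-Whitney test of OSCE B at 12 months with no covariates, so the timing of these variables cannot alter its result.

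**The case against.** The strongest reply is that the timing is unspecified and not fixed late. Item 2b names no visit. Its neighbours, the Birth Register data (2c) and the two-monthly reports (2d), are plainly not tied to months 4 and 9. The list numbering runs i to iv and then b, c, d with no a, so the layout is a weak guide. The schedule table has no confounder row at all, so a blank at month 0 proves little. The exit topics read as ordinary process evaluation and have their own qualitative analysis.

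Much of this stands. A reader might infer that the exit material certainly feeds the confounder table, so that the table does mix baseline and app effects. The protocol does not say so. The matching lists make it the natural reading, but the text supports only that the values can be mixed. Nor is any app effect on these variables shown, and two-monthly reports go to both sites, so feedback is not wholly specific to the app arm.

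Three further inferences are tempting and not supported:
- *That the confounder table is the only check on comparability.* OSCE B at month 0 is another.
- *That late measurement inflates the false-positive rate of the primary test.* Any such inflation would come from a pre-existing hospital difference met by an unadjusted test with one hospital per arm. It would be the same whenever burnout was recorded.
- *That providers who leave early contribute no confounder data.* Since item 2b fixes no visit, this cannot be established.

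The reply does not remove the central point. The heading places collection inside the intervention year, exit is the only specific occasion named for the changeable items, and nothing places any of them before training.

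**Conclusion.** The point holds in a limited form. Followed as written, the protocol yields values taken after allocation for variables that it then treats as potential confounders. Four of the 12 (burnout, motivation, perceived workload, supervision) are the ones chiefly at risk of carrying an effect of the app or feedback, and baseline supervision is in addition a long recall. The fixed provider characteristics and delivery volume are not affected.

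The damage is to the descriptive judgement of whether the hospitals were comparable. It cannot be given a numerical size from the protocol. The primary test is untouched, and with one hospital per arm the app effect stays confounded with hospital even if every variable is measured at baseline. The conclusion rests on two assumptions: that no other study document schedules these items before training, and that the named variables could change within a year.

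**What to change.** - Record the changeable provider-level items (burnout, motivation, perceived workload, patients and areas covered, supervision) by a short questionnaire at the consent contact, which already takes place before training. Ideally this is done before the allocation is known. Because the draw falls just before phase 2 and the protocol does not say whether consent comes before it, the order should be stated. The fixed characteristics can go on the same form.
- Record site-level items (delivery volume, equipment, posted algorithm) for the period just before training.
- Add a month-0 row for these items to the schedule table.
- Use only these values in the confounder comparison under Data Analysis, Phase 2. Report values from months 4 and 9 and from exit separately, as process data.

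The variables stay the same and only their timing changes. The cost is one short questionnaire at an existing contact. The gain is a comparability description that can be interpreted; it does not cure the two-hospital design.

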We will train a minimum of 20 frontline health providers (10 per hospital) from two district hospitals in southwestern Ugandan in HBB 2.0 and ECEB. HBB and ECEB training will be conducted by national trainers in the ratio of 1 trainer to 6 providers. Providers will undergo ECEB training in addition to HBB as these training programs are recommended by the Uganda Ministry of Health to be offered together.

HBB 2.0 training takes place over one day and ECEB training over two days. Participants will be invited from both hospitals to any one episode of training to minimize the number of frontline birth attendants in trainings at any single time.

One hospital will be randomly selected and its providers will have access to the most updated version of HBB Prompt (beta) at the end of the trainings (Intervention arm). The control group will not have exposure to the HBB Prompt app post training.

Participants in both centers will be asked to achieve a minimum practice target of once per day. Our recommended frequency to use the app will be once per shift (i.e. run through 1 simulation per person as a pair). An HBB article from earlier this year showed the greatest improvement when health workers practiced at the beginning of every shift. As it may be difficult to ensure that it is done at the beginning of shift, we will leave the timing of once a shift practice at the discretion of providers. Whenever a new team comes on, they will be recommended to ask the previous team if they did a simulation practice. If not, then they will remind the outgoing team to complete it. These recommendations on frequency of practice will be offered at both the intervention and control sites. All sites will receive resuscitation practice mannequins and a resuscitation practice table.

We will present to the Health Facility team the results of their HBB simulation practice frequency as captured by the HBB Prompt app analytics in the intervention arm. This app analytics data on frequency of practice will be presented to the health facility every two months during the one year study period. The app will be designed to generate both individual and group (facility) practice frequency. Both intervention and control arms will have a standard log-book to record frequency of practice. The accuracy of the log-book will be compared to the data retrieved from app analytics in the intervention arm.

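### The hospital draw is made before training and both month-0 OSCE B assessments, possibly before individual consent, with no concealment, although the app is needed only after training

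*Protocol*

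**What the plan says.** The Randomization section dates the draw: "A random sequence generator will be used to determine a random number just prior to the start of phase 2". An odd number makes one hospital the intervention site and an even number the other, so a single number sets both arms.

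Under Objective 2, the Phase 2a heading leads straight into the HBB 2.0 and ECEB training of at least 10 providers per hospital. Sessions are mixed: "Participants will be invited from both hospitals to any one episode of training". For the selected hospital, "its providers will have access to the most updated version of HBB Prompt (beta) at the end of the trainings".

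Objective 3, item 1, sets the first OSCE B assessments: "At 0 months, (immediately before and after training".

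The enrolment paragraph says that "individual frontline birth attendants will be approached and consented to be part of the study before training sessions are conducted". It does not place consent relative to the draw.

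Data Analysis, Phase 2, lists among the secondary between-arm comparisons "OSCE B scores at 0, 3, and 6 months", and adds a "comparison of OSCE B score after training at 0 months and at 12 months within each arm using the Wilcoxon-signed rank test".

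The protocol does not say who makes or holds the draw, who is told and when, or whether recruiters, trainers, providers or OSCE raters are kept unaware of it.

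**The concern.** With two hospitals and one draw, anyone who knows the number knows the arm of every provider, including those not yet approached. The protocol creates that knowledge earlier than any stated activity requires and does not restrict it. Two things are exposed.

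- **Enrolment.** Providers are approached individually, eligibility is broad, and only a minimum number per hospital is set. If the allocation is known at that stage, it can affect who is approached and who agrees. Those enrolled are the people compared at month 12, by a Mann-Whitney test without baseline adjustment. Provider level, experience and previous training are collected but compared only descriptively.
- **Month-0 scoring.** A rater who knows the arm may score the pre- or post-training OSCE B differently. Month-0 scores are compared between arms, and the post-training score is the reference for the within-arm test against month 12.

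**Working it through.** The protocol states no figure on this point to reproduce. The check is the order of events, then a count, then a look at whether the month-0 data could expose a problem.

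**Order of events**

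1. Draw, just before phase 2 (Randomization).
2. Pre-training OSCE B (Objective 3, item 1).
3. HBB and ECEB training, the first activity under Phase 2a (Objective 2).
4. Post-training OSCE B (Objective 3, item 1).
5. App access at one hospital (Objective 2).
6. Follow-up at 3, 4, 6, 9 and 12 months (Data Analysis, Phase 2).

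Individual consent comes before step 3, on an unstated side of step 1. Step 5 is the first that depends on the draw. A later draw could be read into the Phase 2a sentence on selecting a hospital, but its timing phrase dates app access, whereas the Randomization section dates the draw itself. Placing training before phase 2 would contradict the Phase 2a heading.

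**Scores taken between the draw and the first need for it**

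Inputs: at least 20 providers (Objective 2), and five OSCE B assessments each, namely pre-training, post-training, 3, 6 and 12 months (Objective 3 and the schedule table).

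- All OSCE B scores: 20 × 5 = 100.
- Month-0 scores: 20 × 2 = 40.
- Planned comparisons using them: up to 2 between arms (pre, post) + 2 within arms (post versus 12 months) = 4.

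**Could the month-0 comparison reveal selective enrolment?**

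Assumptions: 10 providers per arm, normally distributed scores, exact two-sided Mann-Whitney test at 0.05, 20,000 simulated trials. The imbalances are a range chosen to show detection, not estimates of bias.

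| True month-0 imbalance | Flagged, no hospital effect | Flagged, ICC 0.05 | Flagged, ICC 0.10 |
|---|---|---|---|
| 0 SD | 4.1% | 9.3% | 14.5% |
| 0.25 SD | 6.9% | 12.4% | 17.6% |
| 0.5 SD | 15.9% | 21.3% | 26.3% |
| 1.0 SD | 51.6% | – | – |
| 1.4 SD | 80.0% | – | – |

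An independent rerun agreed within simulation error. The ICC values are assumed because the protocol gives none. An imbalance of half a standard deviation would usually pass unnoticed. Once hospitals differ at all, a flagged difference could not be told apart from an ordinary difference between the two sites.

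**The case against.** The strongest reply concerns weight, since the order of events is not in dispute.

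- **The harm is conditional.** Nothing says the draw will be disclosed early or that consent will follow it. This stands, and it is why no bias is claimed. But the protocol does not prevent either.
- **There is little reason to enrol by arm.** Both hospitals get the same training, practice recommendations, mannequins and practice table; only the app differs. This limits the incentive without removing it. The number of eligible staff is not given, so the room for selection is unknown.
- **Mixed sessions protect the trial.** They make differential teaching less likely. They protect neither enrolment nor month-0 scoring.
- **Month-0 scores do not enter the primary test.** Correct. The route to month 12 is enrolment; the scoring route reaches only secondary comparisons.
- **Rating at month 0 is inferred.** The phrase "In addition to the OSCE skills checklist as scored by raters" appears under the unannounced month-4 and month-9 visits, not under OSCE B at month 0. That is fair. Human scoring of a checklist at month 0 is a reasonable inference, not a stated fact.
- **The figures do not measure bias.** Also correct. The count shows exposure, and the simulation shows only that the month-0 test is a weak check, on continuous scores where OSCE B is a 23-point scale with ties.
- **Larger problems remain.** One hospital per arm confounds site with app, and nothing masks follow-up rating. Both persist after the fix, but neither is a reason to keep an avoidable weakness.

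**Conclusion.** The concern holds. As written, the allocation is fixed before training and both month-0 OSCE B assessments, possibly before individual consent, with no concealment stated and no stated need for it until app release. At the minimum sample this leaves 40 of 100 planned OSCE B scores, and up to four planned comparisons, open to knowledge of the arm. Selective enrolment, if it occurred, would carry into the month-12 comparison. No size of bias can be derived from the protocol.

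The conclusion rests on reading the Phase 2a heading as the start of phase 2, and on the inference that people score OSCE B at month 0. Timing and concealment of allocation are matters of trial conduct fixed in the protocol, so an unseen SAP does not settle them. This is a worthwhile improvement at low cost. It is not the main limit on what a two-hospital pilot can show.

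**What to change.** In Randomization, replace the present timing with this: the same odd/even draw is made only after providers at both hospitals have consented and had their post-training OSCE B scored, immediately before the app is released. Alternatively, the draw may be made earlier if someone not involved in recruitment, training or rating holds the result until that point. In the enrolment paragraph, state that consent at both hospitals is complete before the allocation is disclosed.

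The draw, visits and staff are unchanged. App set-up at the chosen hospital would follow disclosure, and providers trained in earlier sessions may wait for access. The protocol gives no interval between sessions. If phase 1 takes its planned 4 months and training meets the target of 6 months from project start, all sessions fall within 6 − 4 = 2 months, which bounds the wait under those assumptions. The protocol already places access after the trainings, so the added delay may be small or nil. The change does not address one-hospital-per-arm confounding or knowledge of the arm from month 3 onwards.

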- Demographic data and potential confounders (volume of deliveries, workload in labor and delivery, burnout, motivation, baseline supervision, experience, previous training, provider level, number of patients/areas each provider is responsible for, length of time provider has been in practice, availability of equipment, availability of an HBB algorithm posted at the bedside)
- Other clinical outcomes: death before discharge, admissions to the nursery, number of deliveries, number of infants requiring bagging, fresh stillbirths, neonatal mortality prior to discharge
- Frequency of practice, self vs. group practice, skills practiced

Qualitative data from focus groups and interviews:

- Similar to in phase 1, audio recordings will be transcribed and reviewed using a grounded theory approach. Coded themes and categories will be compared descriptively between participants in the intervention versus the control groups.

Budget Summary

Budget category	Total CAD
Remuneration - funding recipient's employees	35,441
Fees - Subcontractors	19,642
Reimbursable Travel Costs	9,960
Reimbursable Goods and Supplies	9,304
Reimbursable Equipment Costs	2,640
Reimbursable Project Administration Costs	2,845
Sub-grants	20,000
Total Project in CAD	99,831

References

1. Msemo G1, Massawe A, Mmbando D, Rusibamayila N, Manji K, Kidanto HL, Mwizamuholya D, Ringia P, Ersdal HL, Perlman J. Newborn mortality and fresh stillbirth rates in Tanzania after helping babies breathe training. *Pediatrics*. 2013 Feb;131(2):e353-60. doi: 10.1542/peds.2012-1795. Epub 2013 Jan 21.
2. Kc A1, Wrammert J2, Clark RB3, Ewald U2, Vitrakoti R4, Chaudhary P4, Pun A2, Raaijmakers H2, Målqvist M2. Reducing Perinatal Mortality in Nepal Using Helping Babies Breathe. *Pediatrics*. 2016 Jun;137(6). pii: e20150117. doi: 10.1542/peds.2015-0117.
3. Goudar SS1, Somannavar MS, Clark R, Lockyer JM, Revankar AP, Fidler HM, Sloan NL, Niermeyer S, Keenan WJ, Singhal N. Stillbirth and newborn mortality in India after helping babies breathe training. *Pediatrics*. 2013 Feb;131(2):e344-52. doi: 10.1542/peds.2012-2112. Epub 2013 Jan 21.

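### Does leaving theater out of the exclusion criterion make theater birth attendants both eligible and ineligible?

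*Protocol*

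**What the plan says.** In the protocol section Participant eligibility criteria and enrolment, the inclusion criterion covers frontline birth attendants involved in delivering or caring for babies "in the maternity ward, theater or pediatric wards with a possibility of involvement in newborn resuscitation". The exclusion criterion on the next line is "Health workers providing care in other wards other than maternity and pediatrics".

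The same section describes one route into the study for both hospitals. The medical superintendent gives permission, and then "individual frontline birth attendants will be approached and consented to be part of the study before training sessions are conducted".

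Phase 2a sets the size: "We will train a minimum of 20 frontline health providers (10 per hospital) from two district hospitals". One of the two hospitals is drawn at random to receive the app, so hospital and arm coincide. Under Data Analysis, Phase 2, the test is stated as: "Comparison of intervention versus control for the following outcomes will be analyzed at each time point using the Mann-Whitney U test". The primary outcome is the OSCE B score at 12 months. A list of provider and site characteristics is to be compared descriptively between arms.

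**The concern.** Two adjacent criteria define the study population with different lists. Inclusion names three areas (maternity, theater, pediatrics) and exclusion spares two (maternity, pediatrics). Someone who works only in theater seems to satisfy both criteria at once. The exclusion also lacks a word such as *only*, so a very literal reader could bar a maternity midwife who sometimes covers another ward.

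This would normally be trivial, but two features of the trial give it some weight. Because each arm is one hospital, any difference in how the sites read the rule becomes a difference between arms in job type and exposure to resuscitation. The arms are also small, and the stated primary comparison is an unadjusted rank test, which would not correct for such a difference.

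**Working it through.** The protocol gives no figure to reproduce here. The check sets the two criteria side by side for each type of provider, and then asks what would have to happen for the wording to affect the result.

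**Who is affected**

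| Provider | Inclusion | Exclusion | Conflict? |
|---|---|---|---|
| Maternity or pediatric staff only | met | not triggered | none |
| Theater-only birth attendant | met, named explicitly | triggered only if theater counts as an other ward | depends on the reading |
| Maternity or pediatric staff who also cover elsewhere | met | triggered only if any work on a second ward is enough | depends on a strict reading |
| Staff of other wards only | not met | triggered | none |

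The conflict is certain for no group.

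**Which reading the text supports.** The exclusion is limited to *wards*. The inclusion line attaches that word to maternity and to pediatrics and leaves theater without it. The exclusion then spares exactly the two areas that the inclusion line calls wards. On the protocol's own usage theater is not a ward, so the exclusion does not reach it. The explicit naming of theater one line earlier points the same way.

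For cross-covering staff, Objective 3 and the Phase 2 analysis list both include the number of patients or areas that each provider is responsible for. That does not prove that cover of unrelated wards is allowed. It does make it unlikely that a second area of work was meant to exclude anyone.

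**Size if the reading did go wrong.** The input is the minimum of 10 providers per hospital (Phase 2a).

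- Share of an arm per provider: 1/10 = 10%.
- If two or three theater providers were enrolled at one site and none at the other (an assumption; the protocol gives no count of theater staff): 2/10 = 20% to 3/10 = 30%.

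Ten is a minimum, so these shares fall as enrolment rises.

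**What has to happen for harm.** All of the following are needed: the ambiguous reading is adopted; it is adopted at one hospital and not the other; theater-only attendants are among those approached; and theater staff differ from the rest in OSCE B score at 12 months. The protocol documents none of these, and the common enrolment process works against the second.

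**What would show an imbalance.** The descriptive comparison begins "Demographic data and potential confounders (volume of deliveries, workload in labor and delivery, burnout, motivation, baseline supervision, experience, previous training, provider level" and goes on to areas covered and length of time in practice. OSCE B is measured before and after training at month 0 in both arms, so a difference in starting skill would be visible. Work area itself is not on the list, so this protection is partial.

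**The case for a change.** The best case for a change is that an eligibility rule should not depend on whether a reader regards theater as a ward. Eligibility belongs in the protocol and cannot be left to an analysis plan, and one line would settle it. Timing adds to the case. The Randomization section places the draw just before phase 2, while providers consent before the training that opens phase 2. The protocol does not say that enrolment closes before the draw, so loose criteria could leave room for judgement once the allocation is known.

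Part of this stands. The two lists do differ, no other section reconciles them, and aligning them would be tidier. The timing argument carries less weight on this point. If the allocation is known at enrolment, choice over whom to approach remains however clearly the criteria are worded. Likewise, two hospitals can differ in staff mix under perfectly clear criteria, because there is one hospital per arm. Neither problem comes from this sentence, and rewording it would remove neither.

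**Conclusion.** The mismatch is real but clerical. The natural reading, which follows the protocol's own use of *ward* and its explicit mention of theater, admits theater birth attendants, and a study team enrolling at both hospitals would be expected to apply it that way. The largest effect that can be put in numbers is 10% of an arm per discordant provider at the minimum enrolment. The 20% to 30% range rests entirely on assumed counts. No outcome, test or conclusion depends on the wording, so no change to the plan is called for.

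This rests on two assumptions: that both hospitals use the single enrolment process described, and that the explicit naming of theater governs over its omission from the exclusion. Evidence that one site had turned away theater staff while the other enrolled them would reopen the question.
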